### **7.4.2. Complete Response Rate**

Complete response rate is the percentage of participants with a best overall response of CR as defined by revised response criteria for lymphomas ([Cheson et al 2014](#)). For responses as determined by IRC, the best overall response for each participant will be provided by the clinical reviewer. Participants who do not have sufficient baseline or on-study response assessment information to be adequately assessed for response status will be included in the denominators in the calculation of CRR.

The CRR as determined by IRC will be estimated with 95% CIs for all participants and participants who have at least 2 prior therapies in the FAS. Confidence intervals will be calculated based on the exact method for binomial distributions.

A sensitivity analysis of CRR will be provided to summarize participants who switched to the selected treatment regimen after starting the maintenance dose as a separate treatment regimen.

### 7.4.3. Progression-Free Survival

Progression-free survival is defined as the time from the date of the first dose of the study drug to the first documented disease progression as determined by revised response criteria for lymphomas (Cheson et al 2014), or death due to any cause, whichever occurs first. For response assessed by IRC, date of disease progression will be provided by the clinical reviewer. Censoring for PFS will follow the algorithm outlined in Table 2, which is based on FDA Guidance for Industry: Clinical Trial Endpoints for the Approval of Non-Small Cell Lung Cancer Drugs and Biologics (2015) and Guidance for Industry: Clinical Trial Endpoints for the Approval of Cancer Drugs and Biologics (2018).

**Table 2: Evaluation and Censoring of Progression-Free Survival**

Situation	Outcome	Date of Progression or Censoring
No baseline tumor assessments	Censored	Day 1
No valid postbaseline response assessments	Censored	Day 1
Progression documented between scheduled response assessments	Progressed	Date of first overall response of PD
No progression	Censored	Date of last valid radiologic assessment (not NE and not missing)
Study discontinuation for undocumented progression	Censored	Date of last valid radiologic assessment (not NE and not missing)
Study discontinuation for toxicity or other reason	Censored	Date of last valid radiologic assessment (not NE and not missing)
New anticancer treatment started	Censored	Date of last valid radiologic assessment (not NE and not missing) on/before starting a new anticancer treatment
Death before first progressive response assessment	Progressed	Date of death
Death between adequate response assessments	Progressed	Date of death
Death or progression after 2 or more missed assessments	Censored	Date of last valid radiologic assessment (not NE and not missing) before the missed assessments

NE = not evaluable.

The total number of participants whose disease progressed as determined by IRC or who died and the number of participants censored will be summarized. The Kaplan-Meier estimate of median PFS as determined by IRC and its 95% CIs will be provided, with the CIs calculated using the generalization of Brookmeyer and Crowley's method (1982) with log-log transformation (Klein and Moeschberger 1997). Progression-free survival rates at Month 6, 12, 18, 24, and 36 will also be provided with 95% CIs calculated using Greenwood's formula to estimate the standard error.

A sensitivity analysis of PFS will be performed where response assessments after the time of crossover will be excluded from the determination of PFS for participants who switched to the selected treatment regimen after starting the maintenance dose. Crossover participants who have not progressed at the time of crossover will be censored at the last valid radiologic assessment on/before the time of crossover.

The analyses described above will be summarized for all participants and participants who have at least 2 prior therapies in the FAS.

#### **7.4.4. Overall Survival**

Overall survival is defined as the time from the date of the first dose of study drug to death due to any cause. For participants who are still alive at the time of the analysis, OS will be censored on the date the participant is last known to be alive.

The number of participants who died and the number of participants censored will be summarized. The Kaplan-Meier estimate of median OS and its 95% CIs will be presented, with the CIs calculated using the generalization of Brookmeyer and Crowley's method (1982) with log-log transformation (Klein and Moeschberger 1997). Survival rates at Month 6, 12, 18, 24, and 36 will also be provided with 95% CIs calculated using Greenwood's formula to estimate the standard error.

[figure not shown]
The analyses described above will be summarized for all participants and participants who have at least 2 prior therapies in the FAS.

[figure not shown]
#### **7.4.5. Best Percentage Change in Disease Burden**

For each participant with measurable lesions at baseline, target lesion size as measured by sum of product of diameters of all target lesions will be used as the measure for disease burden. For all participants and participants who have at least 2 prior therapies in the FAS, the best percentage change from baseline, defined as the largest decrease in target lesion sizes during the study, will be summarized, and a waterfall plot of the best percentage change will be generated using data from IRC. Note that for participants who only have increases in target lesion sizes from baseline, the smallest increase will be considered as the best change from baseline. For IRC, there will be 2 radiologic reviewers for each participant. An adjudication will be performed per the Independent Review Charter when Reviewers 1 and 2 disagree on the CT/MRI best overall response, or when best overall response is consistent and the date of initial response and/or the date of PD differ between Reviewers 1 and 2. The adjudicator will choose the read that he or she believes most accurately represents the adjudication parameter(s) in question. This is considered the "accepted read," and data from this reviewer will be used for the analysis. When there was no adjudication needed, data from Reviewer 1 will be used for the analysis. An indicator is provided to identify the read that is considered to be the accepted assessment in data from IRC.

[figure not shown]
For splenic MZL participants who have splenomegaly only at baseline, the spleen size as measured by the enlarged portion of the splenic length (ie, splenic length in excess of the 13 cm normal threshold) will be used as the measure for disease burden. The best percentage change from baseline, defined as the largest decrease in spleen size during the study, will be summarized, and the best percentage change using data from IRC will be included in the waterfall plot as described above. Note that for participants who only have increases in spleen size from baseline, the smallest increase will be considered as the best change from baseline.

Best change in disease burden as reported by the investigator will also be summarized as described above for all participants in the FAS. Target lesions considered "too small to measure" will be assigned a default value of 5 mm × 5 mm for purposes of this analysis. Likewise, target lesions identified as "not present" at postbaseline assessments will be assigned 0 mm × 0 mm for this analysis. In the event a target lesion is unaccounted for in a particular postbaseline timepoint (ie, assessment missing or NE), then the overall sum of product of diameters for target lesions will not be evaluable for that postbaseline timepoint.

## 9. SAFETY AND TOLERABILITY

[Appendix A](#) provides a list of planned tables, figures, and listings. Sample data displays are included in a separate document.

### 9.1. General Considerations

Summary tables may be replaced with listings when appropriate. For instance, an AE frequency table may be replaced with a listing if it only contains a few unique PTs reported on relatively few participants.

### 9.2. Adverse Events

#### 9.2.1. Adverse Event Definitions

A TEAE is any AE either reported for the first time or worsening of a pre-existing event after first dose of study drug and within 30 days of the last administration of study drug regardless of starting new anti-lymphoma therapy. Analysis of AEs (as discussed below) will be limited to TEAEs, but data listings will include all AEs regardless of their timing in relation to study drug administration. For purposes of analysis, all AEs will be considered TEAEs unless the AE can unequivocally be defined as not treatment-emergent.

Adverse events will be tabulated by MedDRA PT and SOC. Severity of AEs will be graded using the NCI CTCAE version 4.03. The CTCAE reporting guidelines and grading details are available on the Cancer Therapy Evaluation Program website.

The subset of AEs considered by the investigator to be related to study drug will be considered to be treatment-related AEs. If the investigator does not specify the relationship of the AE to study drug, the AE will be considered to be treatment-related. The incidence of AEs and treatment-related AEs will be tabulated. In addition, serious TEAEs will also be tabulated.

### 9.2.2. Adverse Events of Special Interest

The number of participants who experienced any TEAEs of special interest listed below will be tabulated by maximum severity.

- Colitis
- Diarrhea
- Exfoliative dermatitis
- Febrile neutropenia
- Intestinal perforation
- Rash
- Pneumonitis
- Pneumonia
- PJP infection
- CMV infection
- Herpes simplex
- Varicella zoster virus infection

The time to onset of a TEAE is defined as the interval between the date of first dose of study drug and the date of the first occurrence of a TEAE. Participants who have not experienced a TEAE at the time of analysis will be right-censored at the earlier of 30 days after the last dose date and date of last study visit through the end of safety follow-up. If participants have missing or partial last dose dates of study drug or onset date of a TEAE, the partial or missing dates will be handled using the rules explained in Section 4.1.4.

Summaries of time to onset of new or worsening Grade 3 or higher AEs will be provided using descriptive statistics and the life-table method for rash, colitis, diarrhea, febrile neutropenia, pneumonia, herpes simplex, and varicella zoster virus infection. In addition, summaries of time to onset of new or worsening AEs of any grade will be provided using descriptive statistics and the life-table method for colitis, diarrhea, exfoliative dermatitis, intestinal perforation, pneumonia, pneumonitis, PJP infection, CMV infection, herpes simplex, and varicella zoster virus infection. Kaplan-Meier plots of time to onset of new or worsening Grade 3 or higher AEs will be provided for rash, colitis, and diarrhea. In addition, Kaplan-Meier plots of time to onset of new or worsening AEs of any grade will be provided for colitis and diarrhea.

Descriptive statistics of time to onset of these TEAEs of special interest are based on all participants who have experienced a TEAE at the time of analysis. To summarize these TEAEs of special interest using the life-table method, the effective sample size is defined as the number of participants at the beginning of interval minus half the participants censored in the interval. The conditional proportion is calculated as the number of first events divided by the effective sample size in the interval.

The longest duration of a TEAE of any grade is defined as the longest interval between the date of occurrence of a TEAE and the date of resolution. The longest duration of a Grade 3 or higher TEAE is defined as the longest interval between the date of occurrence of a Grade 3 or higher TEAE and the date of improvement to Grade 2 or lower. If participants have missing or partial onset/end date of a TEAE, the partial or missing dates will be handled using the rules explained in Section 4.1.4. Participants who have missing end date of a TEAE at the time of analysis will be right-censored using the following algorithm:

- If the TEAE is serious, then the participant will be censored at the earlier date of data cutoff, study discontinuation, and death.
- If the TEAE is not serious,
  - If the participant is ongoing with study treatment, then the participant will be censored at the data cutoff date, OR
  - If the participant discontinued treatment, then the participant will be censored at date of safety follow-up visit, or 35 days after the end of treatment visit (or after the last dose if the end of treatment visit was not performed), whichever is later; the censored date will be truncated by the earlier date of data cutoff, study discontinuation, and death if beyond.

Longest duration of new or worsening Grade 3 or higher colitis, diarrhea, rash, and febrile neutropenia will be summarized. In addition, longest duration of new or worsening AEs of any grade will be summarized for colitis, diarrhea, and rash.

The total number of participants whose TEAE of any grade resolved or whose Grade 3 or higher TEAE improved to Grade 2 or lower and the number of participants censored will be summarized. The Kaplan-Meier estimate of median time to resolution/improvement and its 95% CIs will be provided, with the CIs calculated using the generalization of Brookmeyer and Crowley's method (1982) with log-log transformation (Klein and Moeschberger 1997). Resolution/improvement rates at selected timepoints will also be provided with 95% CIs calculated using Greenwood's formula to estimate the standard error.

TEAEs of special interest to be summarized may be adjusted based on emerging data.

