### **9.3.4. Worsening Laboratory Events of Special Interest**

Laboratory events of special interest are listed below.

- ALT increased
- AST increased
- Absolute neutrophil count decreased

The time to onset of a worsening laboratory event is defined as the interval between the date of first dose of study drug and the date of the first occurrence of CTC grade worse than baseline for the laboratory event. Participants who have not experienced a worsening laboratory event at the time of analysis will be right-censored at the last postbaseline study visit with nonmissing CTC grade of the laboratory event.

Time to onset of worsening Grade 3 or 4 laboratory events of special interest will be summarized using descriptive statistics and the life-table method as described in Section 9.2.2, and the Kaplan-Meier plot of time to onset of worsening Grade 3 or 4 absolute neutrophil count decreased will be provided. Laboratory events of special interest to be summarized may be adjusted based on emerging data.

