## Figures

Figure No.	Title
4.1.1	Forest Plot of Objective Response Rate as Determined by Independent Review Committee
4.2.1	Kaplan-Meier Estimates of Duration of Response as Determined by Independent Review Committee
4.2.2	Kaplan-Meier Estimates of Duration of Response as Reported by Investigator
4.2.3	Kaplan-Meier Estimates of Progression-Free Survival as Determined by Independent Review Committee
4.2.4	Kaplan-Meier Estimates of Progression-Free Survival as Reported by Investigator
4.2.5	Kaplan-Meier Estimates of Overall Survival
4.2.6	Waterfall Plot of Best Percentage Change in Disease Burden as Determined by Independent Review Committee
4.2.7	Waterfall Plot of Best Percentage Change in Disease Burden as Reported by Investigator
4.3.1	Kaplan-Meier Estimates of Duration of Response as Determined by Independent Review Committee – Censoring Crossover Participants
4.3.2	Kaplan-Meier Estimates of Duration of Response as Reported by Investigator – Censoring Crossover Participants
4.3.3	Kaplan-Meier Estimates of Progression-Free Survival as Determined by Independent Review Committee – Censoring Crossover Participants
4.3.4	Kaplan-Meier Estimates of Progression-Free Survival as Reported by Investigator – Censoring Crossover Participants
4.5.1	Kaplan-Meier Estimates of Time to Onset of Selected TEAEs of Special Interest
4.5.2	Kaplan-Meier Estimates of Longest Duration of Selected TEAEs of Special Interest
4.6.1	Line Graph of Mean Values Over Time for Selected Laboratory Values (Hemoglobin, Platelet Counts, Leukocytes, Neutrophils, and Lymphocytes)
4.6.2	Kaplan-Meier Estimates of Time to Onset of Selected Worsening Laboratory Events of Special Interest

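### The Kaplan-Meier onset curves for rash, colitis, diarrhea and neutrophil decrease overstate the share of treated participants affected over time; cumulative incidence curves should be added beside them.

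*SAP*

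**What the plan says.** SAP 9.2.1 counts an adverse event as treatment-emergent only if it starts or worsens "after first dose of study drug and within 30 days of the last administration of study drug".

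For time to onset, SAP 9.2.2 says that participants without the event "will be right-censored at the earlier of 30 days after the last dose date and date of last study visit", where visits count through the end of safety follow-up. It then plans two sets of plots:
- Grade 3 or higher: "Kaplan-Meier plots of time to onset of new or worsening Grade 3 or higher AEs will be provided for rash, colitis, and diarrhea".
- Any grade: "Kaplan-Meier plots of time to onset of new or worsening AEs of any grade will be provided for colitis and diarrhea".

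SAP 9.3.4 adds a laboratory curve: "the Kaplan-Meier plot of time to onset of worsening Grade 3 or 4 absolute neutrophil count decreased will be provided". That curve has a separate rule: event-free participants "will be right-censored at the last postbaseline study visit with nonmissing CTC grade of the laboratory event".

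Appendix A lists the adverse event plots as Figure 4.5.1, "Kaplan-Meier Estimates of Time to Onset of Selected TEAEs of Special Interest", and the laboratory plot as Figure 4.6.2. The same sections plan descriptive statistics and life-table summaries of onset. SAP 9.2.2 also plans counts of participants with each event of special interest by maximum severity (Table 3.2.26), and SAP 9.3.2 plans counts of worsening laboratory abnormalities. No cumulative incidence function appears in the readable text.

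**The concern.** Kaplan-Meier gives a censored participant the same later risk as those still under observation. Here the people censored have mostly stopped treatment or died. By the SAP's own definition, someone past the 30-day window cannot have a first treatment-emergent event, and someone who has died cannot have any. They are not event-free people whose onset was missed.

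One minus Kaplan-Meier then answers a hypothetical question: how many would be affected if nobody left treatment. A clinician looking at an onset curve for colitis or diarrhea will usually read it as the share of treated participants affected by that week. These are the main class toxicities, and the plots are the only planned continuous display of their risk over time. Read in that way, the curves would sit above the incidence tables in the same report, with nothing in the titles to explain why.

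**Working it through.** **Plan's own figure.** The SAP states no expected share for these toxicities, so there is nothing to reproduce.

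**Step 1: direction.** Let r be the number at risk and d the number of events at an event time.
- Kaplan-Meier adds K(t−) × d/r, where K falls only at events.
- Aalen-Johansen adds S(t−) × d/r, where S falls at events and also at competing exits.
- S is never above K, so one minus Kaplan-Meier is never below the Aalen-Johansen estimate on the same data. It is strictly above once any event follows a competing exit.

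Example with four participants: one leaves treatment event-free, and later one has the event. Kaplan-Meier gives 1/3. Aalen-Johansen gives 3/4 × 1/3 = 1/4, which is the true share, 1 of 4.

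**Step 2: size, on stated assumptions.**
- From the documents: mean treatment 52 weeks (Protocol synopsis, approximately 52 weeks); 30-day tail, w = 30/7 = 4.29 weeks (SAP 9.2.1); n = 90 (SAP 3.3).
- Assumed: exponential onset (hazard h) and exponential treatment duration (hazard c = 1/52 per week), independent of each other. On-treatment event rate h/(h + c) of 10% or 35%. The 35% is the any-grade diarrhea rate in the earlier monotherapy study (Protocol 1.3), which used other dosing.

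Formulas:
- 1 − KM(t) = 1 − exp(−ht)
- CIF(t) = (1 − exp(−hw)) + exp(−hw) × h/(h + c) × (1 − exp(−(h + c)(t − w)))

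For the 10% case h = (1/52) × 0.10/0.90 = 0.00214 per week. For the 35% case h = (1/52) × 0.35/0.65 = 0.01036 per week.

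| On-treatment rate | Week | 1 − KM | Cumulative incidence | Gap (points) | Gap / SE |
|---|---|---|---|---|---|
| 10% | 52 | 10.5% | 7.2% | 3.3 | 0.8 |
| 10% | 104 | 19.9% | 9.6% | 10.3 | about 1.2 to 1.4 |
| 35% | 52 | 41.6% | 29.7% | 12.0 | 1.8 |
| 35% | 104 | 65.9% | 36.1% | 29.9 | about 2.6 to 3.1 |

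The SE is that of the Kaplan-Meier estimate in simulated trials of 90 participants; its range reflects different assumed data cutoffs. Simulated means agree with the formulas to within about 0.2 points. With the 30-day tail counted, the eventual shares are 10.8% and 37.8%.

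**Step 3: sensitivity to how fast people stop.** Fix the true share at 20% by 24 months, with constant hazards and no tail. One minus Kaplan-Meier then reads:
- 27% if median time to stop or death is 24 months
- 35% if it is 52 weeks
- 65% if it is 122.5 days (the earlier study's median treatment duration, Protocol 1.3)

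For a true share of 10% the readings are 14%, 18% and 37%.

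**Step 4: does stopping alone separate regimens A and B?** Take the 35% case, h = 0.01036 per week, at week 52 without the tail, and vary only mean treatment time.

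| Mean treatment | 1 − KM | Cumulative incidence |
|---|---|---|
| 26 weeks | 41.6% | 19.5% |
| 52 weeks | 41.6% | 27.5% |
| 78 weeks | 41.6% | 31.3% |

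With equal toxicity hazards and independent stopping, the Kaplan-Meier curve does not move. The cumulative incidence curve does.

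**Step 5: neutrophil decrease.** SAP 9.3.4 sets no 30-day limit, so Step 1 does not carry over through the adverse event definition. It carries over through the visit schedule: Protocol Table 7 has no laboratory sampling after the safety follow-up visit, 30 to 35 days after end of treatment. The last graded value therefore falls at about the same point.

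**The case against.** The strongest reply is that the SAP calls these plots time to onset and never says that they estimate the proportion of treated participants affected. No onset medians or landmark rates are planned from them. As a display of on-treatment risk, censoring at the end of the window is coherent. The share affected is reported elsewhere: by maximum severity, by preferred term, and separately for the initial and maintenance dosing periods. The plots are descriptive and carry no hypothesis or decision rule.

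Most of this stands, and it keeps the point small. It does not remove it. The on-treatment reading is nowhere stated or put in a title. The crude tables give no time course, and they run low while participants are still on treatment at the cutoff.

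A reader might also infer more than the documents support:
- **That the curves make A and B differ through discontinuation alone.** Step 4 shows the opposite under independent stopping: the regimen that people leave faster looks safer on the cumulative incidence curve. If stopping is related to toxicity risk, the Kaplan-Meier curve can shift as well. SAP 3.2 plans no statistical comparison of the regimens.
- **That the excess always exceeds sampling error.** It is 0.8 SE for the 10% event at week 52.
- **That Kaplan-Meier should be replaced.** It carries the on-treatment hazard information that the incidence curve loses.
- **That the 30-day rule governs the neutrophil curve.** It does not; SAP 9.3.4 has its own rule.

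**Conclusion.** The point holds as a minor one. Read as the share of treated participants with a treatment-emergent event by a given time, the planned curves for rash, colitis and diarrhea can only err upward. The neutrophil curve has a similar problem under its own rule. Death is not named in either rule; it is censored by implication, at or near the last visit or last graded value.

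The direction does not depend on assumptions. The size does: it needs onset and stopping rates that the documents do not give for these regimens. In the worked cases the excess runs from 3.3 points (10% event, week 52) to about 30 points (35% event, week 104). It approaches zero if toxicity comes before most stops. Two statements in the Protocol argue against assuming that: Section 5.4.4 says that most immune-related events in the earlier study came after the first 9 weeks, and Section 1.3 gives that study's median treatment as 122.5 days.

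**What to change.** In SAP 9.2.2 and 9.3.4, add Aalen-Johansen cumulative incidence curves for the events that now have a Kaplan-Meier onset plot.
- Treat as competing events death without the event, and the end of the event window after permanent discontinuation.
- Censor only participants who, at data cutoff, are still on treatment or within 30 days of the last dose. State separately how to handle anyone alive who is lost to contact inside the window.
- In 9.3.4, define the observation window for the laboratory event, through safety follow-up, so that the competing event has a date.
- Keep the Kaplan-Meier plots only if labelled as on-treatment risk, and adjust the titles of Figures 4.5.1 and 4.6.2.
- Add a note that the two displays are to be read together, because cumulative incidence falls when a regimen is stopped sooner.

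The cost is some SAP wording and a few extra descriptive figures. No new data are needed, and the life-table summaries can stay as they are.

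### Kaplan-Meier resolution rates for adverse events of special interest censor participants at death, so they overstate the proportion who recover if anyone dies with the event unresolved

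*SAP*

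**What the plan says.** SAP 9.2.2 defines two recovery endpoints. For events of any grade (colitis, diarrhea, rash) the endpoint is resolution. For events of Grade 3 or higher it is improvement to Grade 2 or lower, and the set is wider: "Longest duration of new or worsening Grade 3 or higher colitis, diarrhea, rash, and febrile neutropenia will be summarized".

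The censoring rule covers participants whose event has no recorded end: "Participants who have missing end date of a TEAE at the time of analysis will be right-censored using the following algorithm". It has two branches that can end at death:

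- Serious events: "If the TEAE is serious, then the participant will be censored at the earlier date of data cutoff, study discontinuation, and death".
- Non-serious events after treatment discontinuation: a date is set from the safety follow-up visit or the end-of-treatment visit, and then "the censored date will be truncated by the earlier date of data cutoff, study discontinuation, and death if beyond".

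The estimators are Kaplan-Meier throughout. For the median: "The Kaplan-Meier estimate of median time to resolution/improvement and its 95% CIs will be provided". For the rates: "Resolution/improvement rates at selected timepoints will also be provided with 95% CIs calculated using Greenwood's formula to estimate the standard error". SAP Appendix A plans the matching plot, Figure 4.5.2, titled "Kaplan-Meier Estimates of Longest Duration of Selected TEAEs of Special Interest".

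Numbers resolved and numbers censored will be shown, but deaths are not separated within the censored. The visible text gives no competing-risk estimator and no sensitivity analysis for this endpoint.

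**The concern.** Kaplan-Meier censoring assumes that a participant who leaves follow-up could still have the event later, with the same prospects as those who remain. That can be reasonable for data cutoff. It cannot be for death, because a participant who dies with ongoing colitis will never resolve it. The estimator nevertheless passes that participant's weight to those still under observation, and if the last person at risk recovers, the curve ends at 100% whatever the number of deaths.

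The SAP change log for Amendment 1 says the duration summaries were added to understand the safety profile better, including how long class-effect events last. A reader will take a resolution rate at a given day as the share of affected participants who had recovered by then. With few affected participants, one death unresolved can separate the reported figure from that share by several percentage points.

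**Working it through.** The plan states no resolution rate or median, so there is no figure of its own to reproduce. The check compares its estimator, 1 − KM with deaths censored, with the Aalen-Johansen cumulative incidence of recovery with death as a competing event. The documents give neither the number affected, nor the deaths unresolved, nor the recovery times; all three are assumed below.

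**1. A case that can be followed by hand.** Ten participants: one dies unresolved on day 9.5, and nine recover at equal spacing from day 3 to day 40. Two recover before the death and six in all by day 28. No other censoring.

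- Kaplan-Meier: the proportion unresolved is (9/10)(8/9) = 0.800 before the death. The death leaves 7 at risk, and four of them recover by day 28: 0.800 × (6/7)(5/6)(4/5)(3/4) = 0.343. Reported rate: 65.7%.
- Cumulative incidence: 6/10 = 60.0%.
- End of the curve: 100% against 9/10 = 90%.
- Median: day 21.5 on both.

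**2. Constant hazards.** Let r be the recovery hazard (ln 2/14, a median of 14 days) and d the death hazard, with d = r·f/(1 − f), where f is the share who would eventually die unresolved. Then

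- 1 − KM = 1 − exp(−r·t)
- cumulative incidence = r/(r + d) × [1 − exp(−(r + d)·t)]

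| f | Day 28 | Day 56 | Long run | Median (days) |
|---|---|---|---|---|
| 2% | 75.0% vs 74.2% | 93.8% vs 92.2% | 100% vs 98% | 14.0 vs 14.1 |
| 5% | 75.0% vs 72.9% | 93.8% vs 89.9% | 100% vs 95% | 14.0 vs 14.3 |
| 10% | 75.0% vs 70.7% | 93.8% vs 85.9% | 100% vs 90% | 14.0 vs 14.7 |
| 20% | 75.0% vs 65.9% | 93.8% vs 77.5% | 100% vs 80% | 14.0 vs 15.8 |

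Each cell gives Kaplan-Meier first. The rates separate as follow-up lengthens; the median moves by 0.1 to 1.8 days.

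**3. Small samples, simulated.** Fixed numbers die unresolved at times uniform on days 7 to 45. The rest recover exponentially with a median of 21 days, with no other censoring.

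| Affected | Deaths unresolved | KM, day 90 | Cumulative incidence, day 90 | Gap (points) |
|---|---|---|---|---|
| 15 | 1 | 94.4% | 88.6% | 5.8 |
| 15 | 2 | 93.9% | 82.4% | 11.5 |
| 10 | 2 | 92.7% | 75.9% | 16.8 |

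With 20 affected and one death the gap is 4.3 points. With no deaths the two estimates are identical.

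The cumulative incidence column can be checked directly. A participant who does not die has recovered by day 90 with probability 1 − 2^(−90/21) = 94.9%, so the expected value for 15 affected and one death is (14/15) × 94.9% = 88.6%. Taking the standard error as √[p(1 − p)/n] at p = 0.886 and n = 15 gives 8.2 points, so one death produces a gap of 5.8/8.2 = 0.7 standard errors.

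**The case against.** The strongest reply is that the problem may never arise. The size rests wholly on assumed deaths. Protocol 1.3 reports 5 subjects with serious diarrhea and 3 with serious colitis among 72 in the earlier study, and mentions no death from the four toxicities. Scaled to 90 participants, that is 90 × 5/72 ≈ 6 and 90 × 3/72 ≈ 4 serious cases, fewer than the 10 to 20 modelled. SAP 9.2.3 allows a listing instead of a table when 10 or fewer participants appear, so the 10-participant scenario might never yield a published rate. Fatal events are tabulated and listed elsewhere, and no stopping, regimen-selection or efficacy rule uses this summary.

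Most of this stands as a limit on importance. It does not repair the estimator. The affected sets are not confined to serious events, because the rates also cover all Grade 3 or higher and all any-grade events. The fatal-event tables cover events with a fatal outcome, not deaths from another cause while the toxicity was ongoing, and they do not correct the rates.

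Three stronger readings are tempting and are not supported:

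- **That a death raises the reported recovery rate.** It does not. In the hand example, leaving the dead participant out gives 6/9 = 66.7% at day 28, and including that participant gives 65.7%. In the simulation the rate goes from 94.9% with no deaths to 94.4% and 93.9% with one and two. Kaplan-Meier falls, but by much less than the true proportion.
- **That the median is materially shortened.** The calculations above show little movement.
- **That fatal events are certainly censored, or certainly counted as resolved.** The rule applies only where the end date is missing. Protocol 8.1.2 collects end dates and a fatal outcome category, and SAP 4.1.4 can set a partial end date to the date of death. The documents do not say how such a date is classified.

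**Conclusion.** The point holds as an estimator mismatch in a descriptive safety summary. Followed as written, SAP 9.2.2 overstates the proportion who resolve or improve whenever someone dies with the event unresolved and others recover later. The direction follows from the method; the size does not follow from the documents. It is zero with no such death. With 15 affected and a median recovery of 21 days, it is about 6 points at day 90 for one death and about 12 for two, less in larger groups and more in smaller ones. The rates are the quantity at risk, not the median. Nothing here bears on the objective response rate.

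**What to change.** In SAP 9.2.2 and Figure 4.5.2:

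- Treat death before resolution or improvement as a competing event, in both the serious and the non-serious branch.
- Report Aalen-Johansen cumulative incidence at the selected timepoints, with a matching variance estimator for the confidence intervals. Read the median from that curve, and report it as not reached if the curve stays below 50%.
- State that a fatal outcome, or an end date equal to or imputed as the date of death under SAP 4.1.4, is not a resolution.
- Show the number who died unresolved beside the numbers resolved and otherwise censored.
- Keep censoring for data cutoff and for study discontinuation other than death.

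The cost is a few lines of SAP text and a small programming change on data already collected. The resolution rates may look less favourable; if nobody dies unresolved, the point estimates do not change.
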